- A key assumption of the TND is that exposure (here, COVID-19 vaccination) does not impact the probability of selection in the case (a positive test result on a COVID-19 test) or control population (a negative test result on a COVID-19 test). It is possible that vaccinated persons may be less likely to be seek testing in order to become a case than unvaccinated persons. This, if present, would create collider stratification bias via the requirement for testing in a TND, which biases estimates away from the null and may lead to overestimations of VE. 12-14
- Owing to the case-control nature of the design, TND allows for estimation of odds ratios (OR) but not hazard or risk ratios. OR are not directly interpretable as percentage reduction in risk, which is an easily interpretable summary measure of VE. OR with a protective direction of effect (ratio < 1) will underestimate risk, leading to underestimations of VE. 15 A cohort design allows for absolute estimates of risk such as risk differences.

The use of a retrospective cohort study allows for the adoption of design principles of randomized control trials to help mitigate some of these biases.

Cohort identification will begin from the date of EUA or FDA approval for the BNT162b2 formulation. Study follow-up will occur from FDA EUA or approval date until COVID-19 diagnosis or other outcome of interest (hospitalization, emergency department visit, outpatient encounter, end of medical and/or pharmacy enrollment, or death [according to the mortality database]).

In aims 1, 2 and 4, vaccination status will be measured as a time-varying exposure. In aims 3 and 5, vaccination status will be measured as a time-fixed exposure. Exposed person-time begins 14 days after receipt of a BNT162b2 formulation. Unexposed person-time is unvaccinated person-time, as well as 0-13 days after vaccination. The unexposed group will be further stratified by previous vaccination status for relative VE: XBB.1.5 unvaccinated and BA.4/5 vaccinated; XBB.1.5 and BA.4/5 unvaccinated and at least 2 doses of mRNA vaccine (regardless of formulation), never COVID-19 vaccinated.

The full data available, from 01 December 2018, will be used as the look-back period to define patient's characteristics, clinical history, risk factors, and healthcare utilization.

TABLE 2. TARGET TRIAL AND TARGET TRIAL EMULATION

Target Trial Specification ^{16,17}	Target Trial Emulation			
Eligibility criteria				

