8.7.4. Aim 3B

To estimate long-term healthcare resource utilization and costs associated with COVID-19 by vaccination status, age, and site of care.

Exposure: Persons will be considered a COVID-19 patient if they experienced a COVID-19-related encounter, regardless of setting (cases). COVID-19 patients (cases) will be matched to 4 patients

without a COVID-19 diagnosis (controls) using the matched index date. Controls may or may not have had health care encounters during the study period. Cases and controls will be matched based on age, sex, insurance type, previous Charlson Comorbidity Index (CCI), number of previous hospitalizations, and follow-up time. The CCI and number of hospitalizations were calculated by using diagnoses during pre-index. For stratification/subgroup analyses, adult persons will be considered vaccinated if they received the BA.4.5 dose 14 or more days prior to index, persons will be considered unvaccinated if they had not received any COVID-19 vaccination doses. Children will be considered vaccinated if they received the any COVID-19 vaccination dose 14 or more days prior to index and will be considered unvaccinated if they had not received any COVID-19 vaccination doses.

Study Period (data including pre-index and follow-up): 01 June 2021 – 31 August 2023

Patient identification (index) window: June 2022 - November 2022

Follow-up time: starting 30 days after first COVID-19 diagnosis (index date) with follow-ups of 1 month, 3 months, 6 month, and 9 months.

Outcomes of interest: Similar to those in Pike et al, 2023

[figure not shown]
- All-cause direct healthcare costs (medical and pharmacy)
- All-cause Healthcare resource utilization
- COVID-19-related hospitalization (for cases only)

Statistical Methods: All analyses will be pooled across California and Louisiana, and stratified by state. Descriptive statistics will be used to summarize patient characteristics, with mean (standard deviation) or median (25th percentile – 75th percentile) for continuous variables and counts (percentages) for categorical variables. A regression model will be developed that adjusts for age, sex, and baseline comorbidities. We will stratify outcomes by vaccination status, healthcare cost (medical and pharmacy), and sites of care (inpatient, outpatient, etc.).

8.7.5. Aim 4

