At least two prior doses of mRNA vaccine and no bivalent BA.4/5 COVID-19 vaccine	-Descriptive -Subgroup	Where the BNT162b2 XBB.1.5 vaccine is the exposure of interest. Using all-available lookback data, received at least two prior doses of mRNA vaccine (regardless of formulation) and did not receive bivalent BA.4/5 COVID-19 vaccine. Yes or No
		Note: the doses must be at least 21 days apart. The list of codes is provided in the Protocol Annex
Never COVID-19 vaccinated	-Descriptive -Subgroup	Using all-available lookback data, no prior receipt of a COVID-19 vaccine (regardless of formulation)
		Note: Patients without prior bivalent BA.4/5 COVID-19 vaccine and either a single mRNA vaccine dose or two mRNA doses less than 21 days apart are categorized as "No", as per Section 5.2.3.
		Yes or No The list of codes is provided in the Protocol Annex
Time since last COVID-19 vaccine	-Descriptive -Subgroup	Using all-available lookback data, time in months between index date and prior receipt of a COVID-19 vaccine (regardless of formulation) The list of codes is provided in the Protocol Annex

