
Variable	Role	Data source	Operational definition
			period. Reported as counts and percentages. Note: Death information is available and is sourced from over 40,000 public and private sources nationally. The coverage rate, estimated at over 90% of CDC reported deaths through present day, is based on the number of deaths in the Fact of Death Mortality Index compared to the number of deaths reported by the CDC. Due to HIPAA privacy restrictions, date of death is reported as month and year. Cause of death is not available.

COVID-19 Vaccination Status:

The exposure of interest is the BNT162b2 Bivalent vaccine.

A patient will be considered vaccinated from 14 days after their vaccination date.

The source of the exposure variables are the California and Louisiana vaccine registries and the HealthVerity claims database. Clinical Vaccines Administered code (CVX), National Drug Codes (NDC) and Current Procedural Terminology® (CPT) codes.

BNT162b2 Bivalent vaccinations will be enumerated using the following hierarchical definition:

- Any person in HealthVerity claims data who has a record in the California/Louisiana Immunization Registry with a CVX code indicating having received the BNT162b2 Bivalent vaccine will be considered vaccinated 14 days after registry event date.
- 2. Any person in HealthVerity claims data who does not have a record in the California/Louisiana Immunization Registry but has a pharmacy claim with an NDC code indicating an BNT162b2 Bivalent vaccine dose will be considered vaccinated 14 days after claim date.
- 3. Any person in HealthVerity claims data who does not have a record in the California/Louisiana Immunization Registry and does not have a pharmacy claim with an NDC code indicating an BNT162b2 Bivalent vaccine dose but has a medical claim with a CPT code indicating an BNT162b2 Bivalent vaccine dose will be considered vaccinated 14 days after claim date.

4. Any person in HealthVerity claims data who does not have a record in the California/Louisiana Immunization Registry, does not have a pharmacy claim with an NDC code indicating an BNT162b2 Bivalent vaccine dose and does not have a medical claim with a CPT code indicating an BNT162b2 Bivalent mRNA vaccine dose will be considered BNT162b2 Bivalent unvaccinated.

Patients will be categorized into the following groups based on their COVID-19 vaccination status:

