- BNT162b2 Bivalent mRNA Vaccine: Patients who received at least one dose of a BNT162b2 Bivalent mRNA vaccine in the baseline period, at least 14 days prior to the index date.
- No Vaccine: Patients who did not receive any COVID-19 vaccines in the up to 12 months prior to the index date. For patients with baseline periods of less than 12 months, all available records in the past up to 12 months periods will be searched.
- Other Vaccines: Patients who were not in the above described 2 vaccination groups. They may include patients who received any type of COVID-19 vaccine in the up to 12 months prior to index date, but did not meet the BNT162b2 Bivalent Vaccine group requirements described above. Some examples of these include patients 1) who had other types of mRNA COVID-19 vaccine and no doses of a BNT162b2 Bivalent vaccine in the baseline period; 2) who received non-mRNA vaccines, etc.

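### The Aim 3B SAP counts people whose only COVID-19 doses are over 12 months old as No Vaccine, and replaces the protocol's any-dose rule for children with bivalent only, without identifying either change

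*SAP*

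**What the plan says.** **Protocol, section 8.7.4.** Vaccination status is defined for the stratified and subgroup analyses. Adults are vaccinated if they had the BA.4/5 dose at least 14 days before index; "persons will be considered unvaccinated if they had not received any COVID-19 vaccination doses". Children have their own rule: "Children will be considered vaccinated if they received the any COVID-19 vaccination dose 14 or more days prior to index". A child with no dose is unvaccinated.

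**Aim 3B SAP, section 5.3 (COVID-19 Vaccination Status).** The SAP states that "The exposure of interest is the BNT162b2 Bivalent vaccine" and forms three groups with no separate rule for children:

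- Bivalent: "Patients who received at least one dose of a BNT162b2 Bivalent mRNA vaccine in the baseline period", at least 14 days before index.
- No Vaccine: "Patients who did not receive any COVID-19 vaccines in the up to 12 months prior to the index date". The search is capped at 12 months even where older records exist.
- Other Vaccines: everyone in neither of those groups.

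**Aim 3B SAP, section 5.6.** The stratification compares Bivalent with No Vaccine and leaves Other Vaccines out. Vaccination status is also a covariate in the regression models.

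**Lookback.** The protocol gives two starting points. Section 8.7.4 has "Study Period (data including pre-index and follow-up): 01 June 2021 – 31 August 2023". Section 8 says "The full data available, from 01 December 2018, will be used as the look-back period", for patient characteristics, clinical history, risk factors and utilization. For the never-vaccinated group, Table 5.3 of the Aim 2 SAP reads "Using all-available lookback data, no prior receipt of a COVID-19 vaccine (regardless of formulation"), and Table 5.3 of the Aim 1 SAP uses the same lookback.

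**The concern.** Results by vaccination status are part of the Aim 3B objective (protocol section 7; Aim 3B SAP section 4). A reader of a No Vaccine cost table will take the label to mean what the protocol says, which is no doses. Under the SAP it means no dose recently. Because Other Vaccines takes only the remainder, a person whose doses are all older than 12 months is placed in No Vaccine, not in Other Vaccines. Two people with the same vaccination history can then be classified differently only because they were indexed in different months.

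For children, the bivalent-only rule changes who can be called vaccinated. A child with only recent wild-type doses is vaccinated under the protocol. Under the SAP the child is in Other Vaccines and leaves the stratified comparison. At the youngest ages, the bivalent vaccine was not authorized until after the index window had closed.

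**Working it through.** The plan states no size for the vaccination strata, so there is no figure to reproduce. The check is date arithmetic.

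**Inputs**

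- Index window: 1 June to 30 November 2022 (Aim 3B SAP section 5.2), which is 30 + 31 + 31 + 30 + 31 + 30 = 183 days.
- First BNT162b2 wild-type authorization (protocol Table 1): 11 December 2020 at 16+; 10 May 2021 at 12–15; 29 October 2021 at 5–11; 17 June 2022 at 6 months to 4 years.
- Bivalent authorization (protocol Table 1): 31 August 2022 at 12+; 12 October 2022 at 5–11; 8 December 2022 at 6 months to 4 years.
- 12 months = 365 days. Because the Aim 3B SAP generally counts a month as 30 days (section 5.6), 360 days is shown as well.

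**Step 1. The No Vaccine cut-off.** Cut-off = index date − 365 days. It runs from 1 June 2021 (index 1 June 2022) to 30 November 2021 (index 30 November 2022). Example: someone last dosed on 15 July 2021 is 335 days from that dose if indexed on 15 June 2022 (Other Vaccines), and 488 days if indexed on 15 November 2022 (No Vaccine).

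**Step 2. Recorded dosing time that the SAP ignores.** Ignored days = cut-off − start of dosing data, not below 0.

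| Start of dosing data | 365-day lookback | 360-day lookback |
|---|---|---|
| 1 June 2021 (protocol 8.7.4) | 0 to 182, mean 91; above 0 on 182 of 183 index days | 5 to 187 |
| 11 December 2020 (first authorization, if the protocol section 8 lookback covers vaccination) | 172 to 354, mean 263; above 0 on all 183 | 177 to 359 |

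By age, on BNT162b2 dates and all available data, a previously vaccinated person can be classed as No Vaccine as follows:

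- Age 12 and over: all 183 index days. At 12–15 the ignored time is 22 to 204 days.
- Age 5–11: 32 index days (30 October to 30 November 2022), or 37 with 360 days.
- Under 5: none, because the first dose date of 17 June 2022 is never more than 12 months before index.

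**Step 3. Index days on which a child can count as vaccinated.** Earliest qualifying index date = authorization date + 14 days; days are counted from then to 30 November 2022.

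| Age | SAP, bivalent only | Protocol, any BNT162b2 dose |
|---|---|---|
| 12–17 | from 14 September 2022: 78 (42.6%) | 183 |
| 5–11 | from 26 October 2022: 36 (19.7%) | 183 |
| Under 5 | 22 December 2022, 22 days after the window closes: 0 | from 1 July 2022: 153 (83.6%) |

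Having only year of birth does not rescue the last row: a child whose calendar-year age in 2022 is 4 or less is truly under 5.

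**The case against.** **The SAP may change the plan.** Protocol section 8.7 allows this and asks for an amendment only for major changes to primary endpoint definitions or their analyses. Aim 3B is a secondary objective. This stands: the changes are not prohibited. But the SAP neither identifies them as changes nor gives a reason, and the label No Vaccine no longer describes the group.

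**Twelve months is a defensible lookback.** It matches the adult baseline, and 1 June 2021 is exactly 12 months before the first index date. On that reading the protocol and SAP agree on the first index day. They part on the other 182. A recency rule would reasonably separate a dose 11 months old from one 16 months old, but neither document says that recency is the intended exposure. Index year-month in the regressions does not undo the misclassification, and the stratified tables do not have it.

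**Stronger readings that the documents do not support**

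- *A planned under-5 vaccinated table will be empty.* Section 5.6 lists age group and vaccination status as separate stratifiers and does not say they are crossed. What holds is that under-5s can enter the vaccination stratification only as No Vaccine, apart from miscoded or off-authorization records.
- *The SAP ignores 172 to 354 days of dosing.* This needs the general lookback in protocol section 8 to cover vaccination status, which that sentence does not name. The 0 to 182 day figure does not need it.
- *A stated share of the No Vaccine group was in fact vaccinated.* Protocol section 8.5 gives 63% with any dose and 16% with a bivalent dose, but for the whole claims population and not at the Aim 3B index dates. No document says how many people had only older doses.
- *The adult bivalent group, possible only from 14 September 2022 while No Vaccine runs from 1 June, is a further SAP error.* It follows from the protocol's own adult rule and is partly handled by the ±14-day case-control match and the index year-month covariate. It is a caution for interpretation and does not require a change.

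**Conclusion.** The concern holds as a misclassification written into the Aim 3B vaccination-status variable. Followed literally, the SAP puts people with only older doses into No Vaccine, in both the stratification and the regression covariate, with a cut-off that moves by six months across the index window. On the reading most favourable to the SAP (data from 1 June 2021, 365 days), 0 to 182 days of recorded dosing are ignored; the figure is larger if all available lookback applies to vaccination status. Separately, the pediatric rule reduces the index days on which a child can be vaccinated to 78, 36 and 0, from 183, 183 and 153.

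These are calendar days, not people; the number affected cannot be computed from the documents. The any-dose counts use BNT162b2 dates only, because no other brand's dates are given. The main Aim 3B comparison, COVID-19 patients against controls, does not define its groups by vaccination status and is not called into question.

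**What to change.** 1. **All ages.** Define No Vaccine as no COVID-19 dose in any available registry or claims record before index. State the lookback start for vaccination history, so that 1 June 2021 (protocol 8.7.4) and 1 December 2018 (protocol section 8) are reconciled.
2. **Adults.** Place people with only older or non-bivalent doses in Other Vaccines.
3. **Children.** Restore the protocol rule: any dose 14 or more days before index, against no dose. A child with only older doses is then vaccinated, not in Other Vaccines.
4. **Models and strata.** Vaccinated would then mean bivalent in adults and any dose in children, so run the vaccination-status stratification and the regressions separately for the two. One pooled covariate would mix two definitions.

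If the sponsor prefers to keep either SAP rule, the SAP should say that it departs from the protocol and why, and the No Vaccine label should be changed to describe the 12-month rule.

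The cost is SAP wording, re-derivation of one variable from data already held, and separate adult and pediatric models. The downsides are a smaller No Vaccine stratum and a pediatric vaccinated group that mixes formulations and brands, as the protocol's rule implies. No index dates are lost.

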5.4. Data Sources

The source of the exposure variables are the California and Louisiana vaccine registries and the HealthVerity Claims database. Containing only de-identified data, the HealthVerity database is Health Insurance Portability and Accountability Act (HIPAA) compliant.

5.5. Study Size

It is expected that there are more than 50,000 potential COVID-19 patients for this study in the data source.

Given the expected number of COVID-19 patients in the study, power calculations were conducted for costs under various scenarios using two-part models. The following assumptions were made: 50% of cases have zero costs, 60% of controls have zero costs, 4 controls matched to each case and a significance level of 0.05. Under various levels of standard deviation (\$10,000 and under), means of non-zero costs among the controls (\$100 and over) and relative differences in costs between cases and controls (1.15 and over), power exceeded 0.99. Therefore, even after

accounting for potential dropout and the use of robust standard errors due to matching, this sample size is sufficient for the study's purpose.

5.6. Data Analyses

Descriptive statistics will be utilized to summarize patient demographic and clinical characteristics in addition to the measured HCRU and cost outcomes. Counts and percentages will be reported for categorical variables. Continuous variables will be summarized using minimum, maximum, median (Q1-Q3) and mean (SD).

All cost measurements will be adjusted to 2024 USD using Consumer Price Index medical care component.

All study measurements will be compared between the COVID-19 and Control cohorts.

HCRU and Cost Outcomes at Different Time Periods:

For HCRU and cost outcomes, all measurements will be provided for the following time periods:

- Post-acute phase: 1-11 months (measured starting from 30 days after the index date)
 - 1 to <2 months (1 month post-acute period)
 - 1 to <4 months (3 month post-acute period)
 - 1 to <7 months (6 month post-acute period)
 - 1 to <10 months (9 month post-acute period)
 - 1 to <12 months (11 month post-acute period)

Within this study, 1 month is generally considered to be equivalent to 30 days, unless otherwise specified.

NOTE: HCRU and cost will not be measured during the acute phase of 0 to <1 month after the index date since this is not within the study scope.

Stratification Analysis:

Patients will be further stratified by the following variables:

Age group:

 Among the overall study population, patients will be stratified by their age at the index date as follows:

- Adult and Pediatric
 - Adult: Patients ≥ 18 years at the index date.
 - Pediatric: Patients 6 months to < 18 years at the index date.
- Detailed Age Groups
 - Adult: 18 29, 30 49, 50 64, 65 74, 75+ years
 - Pediatric: 0 < 2, 2 4, 5 11, 12 < 18 years.
- COVID-19 Vaccination Status:
 - BNT162b2 Bivalent mRNA Vaccine
 - No Vaccine
 - NOTE: Other Vaccines sub-group for vaccination status will not be used for this stratification analysis.
- Site of Care: COVID-19 Hospitalization Status Within 30 Days (Yes/No):
 - Yes
 - No
- ICU Admission (Yes/No) Within 30 Days:
 - Among the overall study population, patients will be stratified by status of ICU Admission (Yes/No) – Within 30 Days
- IMV Usage (Yes/No) Within 30 Days:
 - Among the overall study population, patients will be stratified by status of IMV usage (Yes/No) – Within 30 Days

Sensitivity Analysis:

Sensitivity analyses planned for the study will include:

1. COVID-19 reinfection: In the sensitivity analysis, a COVID-19 patient's follow-up period may be further censored at the first COVID-19 reinfection date (if any). The COVID-19 reinfection is defined as another COVID-19 diagnosis at least 90 days of gap after the previous COVID-19 diagnosis. The study measurements among the overall patient population (without stratifications) will be reported for this sensitivity population.

2. **Open-source Cost:** A portion of patients will have claims data that is linked to open-source cost information. A sensitivity analysis of the overall study analysis (not including the stratification analyses) will be carried out among such linked patients. The open-source cost data will be used to represent the cost information in this sensitivity analysis.

Statistical Analysis:

Descriptive Statistics:

Descriptive statistics will be utilized to summarize patient demographic, clinical characteristics, and HCRU and cost outcomes. Counts and percentages will be reported for categorical variables. Continuous variables will be summarized using minimum, maximum, median (Q1-Q3) and mean (SD). The count and percentage of patients with missing data will be reported.

Comparison Statistics:

All study measurements will be compared between the COVID-19 and Control cohorts. Standardized mean differences (SMD) will be reported for all variables.

Regression Analysis:

Multivariable regression analysis will be used to evaluate the potential predictors of long-term HCRU and costs associated with COVID-19.

- 1. The dependent variables of such regression models will include: number of all-cause hospitalizations during the follow-up period, total cost (charge and allowed amount) of all-cause hospitalizations during the follow-up period, number of COVID-19 hospitalizations during the follow-up period, total cost (charge and allowed amount) of COVID-19 hospitalizations during the follow-up period, total cost (charge and allowed amount) of all healthcare claims during the follow-up period, and total cost (charge and allowed amount) of COVID-19-related healthcare claims during the follow-up period.
